8 STATISTICS AND DATA ANALYSIS

8.1 Sample Size

As previously stated, this is an exploratory biomarker study involving measuring biomarkers of fibrosis in airway mucosal samples (nasosorption and bronchosorption) collected from patients with probable IPF and sarcoidosis compared to healthy volunteers. It is not possible to perform a sample size calculation at this stage, since we do not currently know the magnitude of biomarker differences in nasosorption and bronchosorption samples. Having performed this study, it is hoped that on the basis of particular biomarkers in defined

airway mucosal samples, we can provide sample size calculations for future studies of airway biomarkers in IPF.

8.2 Interim Analysis

The total study involves a total of 30 subjects with probable IPF, 15 patients with sarcoidosis and 15 healthy volunteers. Recruitment for this study is likely to take between 12 and 24 months. An interim analysis at 12 months will be able to identify any emerging differences in biomarkers between the groups, and allow the nature of biomarkers of inflammation to be adjusted prior to the final analyses. In an exploratory study of novel methods of mucosal sampling in probable IPF and sarcoidosis, we do not know the rate of recruitment, and would prefer not to specify an exact number of patients for when interim analysis is performed.

8.3 Statistical Analysis

Data and all appropriate documentation will be stored for up to 10 years after the completion of the study, including the follow-up period.

The major data will be levels of mediators: periostin, surfactant protein (SPD), CCL18 and CXCL13 in blood and bronchial lining fluid.

We shall perform a test of distribution of data (Shapiro-Wilks test) to check normality of data to ensure appropriate statistical tests are applied to the data.

We shall make individual x-y plots for mediators displaying levels for each individual subject within the patient groups (Probable IPF and sarcoidosis) and healthy controls

Summary Statistics

- Normal data with graphs with means and standard error of means (SEM)
- Non-normal data with graphs with medians, quartiles and ranges (box-whisker)

Paired or unpaired t-tests/ANOVA (or equivalent non-parametric tests) will be used to compare mediator levels in blood and airway mucosal lining fluid within groups over time or between different groups at a single time point.

Correlations will be performed to compare mediator levels in blood, and upper and lower airway mucosal lining fluid samples and clinical parameters in patient groups and healthy controls.

Other graphical and analyses methods like heat maps, violin plots, clustering, multivariate analyses and ROC curves will be used as appropriate.

A *P* value of <0.05 is considered significant.

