3.2 Primary Outcome

Comparison of bronchial lining fluid levels of biomarkers/mediators (periostin, surfactant protein D (SPD), CCL18, CXCL13) in patients with IPF and sarcoidosis.

- Determination of level of significance in the levels of the bronchial mediators between IPF and sarcoidosis patients.

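### Section 8.3 lets a normality test choose the analysis mediator by mediator and plans no between-group estimate or confidence interval in either branch

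*Combined protocol and SAP*

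**What the plan says.** The primary outcome (section 3.2) compares four bronchial mediators, periostin, SPD, CCL18 and CXCL13, between two patient groups: "Determination of level of significance in the levels of the bronchial mediators between IPF and sarcoidosis patients". The group sizes are in section 8.2: "The total study involves a total of 30 subjects with probable IPF, 15 patients with sarcoidosis and 15 healthy volunteers". Healthy volunteers have no bronchial sampling, so the primary comparison is 30 v 15.

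The choice of test is in section 8.3. The normality check comes first: "We shall perform a test of distribution of data (Shapiro-Wilks test) to check normality of data to ensure appropriate statistical tests" are used. Then: "Paired or unpaired t-tests/ANOVA (or equivalent non-parametric tests) will be used to compare mediator levels in blood and airway mucosal lining fluid". A P "value of <0.05 is considered significant".

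The same section plans graphs with means and SEM for normal data. For the rest it plans: "Non-normal data with graphs with medians, quartiles and ranges (box-whisker"). Individual-subject plots are also planned, and ROC curves are listed for use where appropriate.

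Section 8.1 gives no sample size calculation, because the size of the biomarker differences is unknown. It hopes that afterwards "we can provide sample size calculations for future studies of airway biomarkers in IPF".

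**The concern.** Three things are left to the data or left open.

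- **The test.** Section 8.3 does not say whether Shapiro-Wilk is run per group, on pooled data or on residuals, or at what level. It does not say whether the t-test is pooled or Welch, or whether levels are logged.
- **The scale.** Each mediator is routed separately. One primary mediator could be reported as a difference in raw means and another as a rank comparison with medians, so the four results could not be set side by side.
- **The estimate.** Neither branch has a between-group effect or a confidence interval. For a study that starts from not knowing the size of the differences, that is the most useful output, and it is what the hope in 8.1 depends on.

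A secondary question is whether the rule keeps its nominal 5% at 30 v 15 when the two diseases differ in spread.

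**Working it through.** The documents give no power, effect size or SD, so there is no planned figure to reproduce.

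**1. What each branch delivers (section 8.3 against 8.1)**

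| Branch | Planned summary | SD available? | Between-group effect and CI? |
|---|---|---|---|
| Normal | mean, SEM | yes, SD = SEM × √n | no |
| Non-normal | median, quartiles, range | not directly; a rough log-scale SD from the quartiles if lognormality is assumed | no |

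A ROC area would be an effect measure, but it is not tied to any endpoint.

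**2. How often the four mediators would take different tests**

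Let p be the chance that a mediator goes to the rank test (Shapiro-Wilk at 0.05 in each group; either failure sends it there). For four independent mediators, P(not all the same test) = 1 − p⁴ − (1−p)⁴. The values of p are simulated at 30 v 15.

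- Normal, equal SDs, p = 0.097: 1 − 0.0001 − 0.665 = 0.335.
- Lognormal, log-SD 0.5 in both groups, p = 0.834: 1 − 0.484 − 0.001 = 0.515.
- Lognormal, log-SD 0.5 (IPF) and 1.0 (sarcoidosis), p = 0.950: 1 − 0.8145 = 0.185.
- Lognormal, log-SD 1.0 in both groups, p = 0.999: 1 − 0.996 = 0.004.

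The ceiling, at p = 0.5, is 1 − 2/16 = 0.875, which is approached at log-SD 0.3. Mixing is common with mild skew and rare with strong skew.

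**3. Type I error of the two-stage rule**

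Inputs: n = 30 and 15 (8.2) and alpha 0.05 (8.3), taken as two-sided. Assumed: Shapiro-Wilk per group at 0.05; Mann-Whitney if either group fails, otherwise pooled t; lognormal data with equal medians; the log-SDs shown. There were 20,000 replicates, with Monte Carlo SE near 5% of √(0.05 × 0.95/20,000) = 0.0015.

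| log-SD IPF : sarcoidosis | Two-stage | Mann-Whitney alone | Welch on logs |
|---|---|---|---|
| 0.5 : 0.5 | 0.053 | 0.049 | 0.049 |
| 1.0 : 1.0 | 0.049 | 0.049 | 0.050 |
| 0.7 : 1.05 | 0.070 | 0.068 | 0.051 |
| 0.5 : 1.0 | 0.097 | 0.087 | 0.052 |
| 1.0 : 0.5 | 0.030 | 0.029 | 0.045 |

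Further runs of 6,000 replicates, with IPF log-SD 0.5 to 1.0, gave 0.068 to 0.081 at a ratio of 1.5 and 0.081 to 0.092 at a ratio of 2. With IPF the more variable group, other runs gave up to 0.039.

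**4. Where the departure comes from**

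- With equal spreads the whole rule stays at 0.049 to 0.053, so the pre-test adds little.
- For normal data at SD ratio 1:2, pooled t alone gives 0.113, Mann-Whitney alone 0.087, the two-stage rule 0.116 and Welch 0.053.
- Reading t-test as Welch inside the rule gives 0.061 for those normal data. It still gives 0.089 for lognormal data at 0.5 : 1.0, because 95% of datasets go to Mann-Whitney.

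**5. Power**

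With equal log-SDs and a shift of 0.9 SD, Welch on logs has 0.783 to 0.787 and the two-stage rule 0.769 to 0.776. At 0.91 SD, Welch on logs has about 79% and the two-stage rule about 78% to 81% across runs.

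**The case against.** The strongest reply is that the study is openly exploratory. A departure of a few points from 5%, in a direction nobody knows, changes little. Individual values will be plotted and data kept for up to 10 years, so log-scale SDs and ratios could be computed later. The summary bullets describe graphs and need not be the full reporting. ROC areas may also be produced. All of this is fair, and it is why the type I error result is only secondary. It does not fill the gap: being computable later is not a commitment, and an exploratory study has most to gain from estimates with intervals.

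Two limits of the simulation also stand. Equal medians with unequal log-SDs imply unequal raw means; at 0.5 : 1.0 the ratio is exp((1 − 0.25)/2) = 1.45. A rejection by the raw-scale t-test is therefore not a false positive for mean levels. And Welch on logs holds 5% here on data generated as exactly lognormal.

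A reader might go further and infer the following, which the documents do not support:

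- *That the rule inflates type I error whenever spreads differ.* If IPF, the larger group, is the more variable, the rule is conservative. The documents give no spreads.
- *That the plan specifies an equal-variance t-test.* It says "Paired or unpaired t-tests/ANOVA (or equivalent non-parametric tests") and leaves the variance form open.
- *That the pre-test causes the error.* The main cause is rank and pooled tests under unequal spread with unequal n.
- *That the study exists to supply sample size inputs.* Section 8.1 states a hope; the primary outcome is the IPF v sarcoidosis comparison.

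**Conclusion.** The point holds as a gap in pre-specification and reporting. The test, its variance form and its scale are not fixed for the four primary mediators, and no between-group effect or confidence interval is planned for any of them. This rests on the text alone and affects both branches. It falls hardest on mediators judged non-normal, where no SD is planned either.

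The chance of mixed tests across the four mediators runs from under 1% to the 87.5% ceiling, depending on skew and assuming independence. The high values belong to mild skew with equal spreads, where type I error is close to 5%. Mixing and error inflation should therefore not be added together as if they came from one scenario.

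Type I error is about 5% with equal spreads, about 7% to 9% (9.7% at one setting) if sarcoidosis has 1.5 to 2 times the log-SD of IPF, and about 3% to 4% in the reverse case. The spread ratios, the lognormal shape and the way Shapiro-Wilk is applied are all assumptions.

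**What to change.** Rewrite section 8.3 to pre-specify, for every mediator:

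- comparison on the log scale with Welch's t-test;
- the ratio of geometric means with its 95% CI;
- the log-scale SD in each group;
- the rank test as a sensitivity analysis, noting that it too is affected by unequal spread when group sizes differ;
- Shapiro-Wilk for description only, not to select the test.

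The log step matters as much as the Welch step: Welch on raw lognormal values at log-SD 1.0 : 0.5 rejected in 17.5% of runs with equal medians, because the raw means differ.

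The cost is wording only, with no extra patients, samples or assays. With equal spreads there is no material loss of power.

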3.3 Secondary Outcomes

1. Comparing mediator levels between airway samples (nasosorption and, bronchosorption) within and across the 3 groups (probable IPF, sarcoidosis and healthy controls). Establish significance between groups and correlations across patient groups for sampling types.
2. Comparing mediator levels and mRNA (gene expression) in blood with airway mediator levels across the 3 patient groups, and assessing the degree of correlation.

3. Comparing mediator levels in airway samples and blood with clinical parameters
4. Comparing urine metabolites across the 3 patient groups.

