4.2 Patient Population

Patients diagnosed with probable IPF and Sarcoidosis will be included. Patients with probable IPF and Sarcoidosis will be selected from clinic lists for patients undergoing bronchoscopy as part of their clinical assessment, and they will be invited to participate in this study that involves additional sampling for clinical research purposes.

Probable IPF patients must have Usual Interstitial Pneumonitis (UIP) on CT scan and will be sub classified by gas transfer (DLco corrected for haemoglobin as detailed below;

- Mild (DLco>60)

- Moderate (DLco 40-60)
- Severe (DLco<40)

Healthy volunteers (age/sex matched, non-smoking, without a clinical history of atopy).

The patient populations will include:

- Probable Idiopathic Pulmonary Fibrosis (IPF), n=30
- Sarcoidosis patients, n=15
- Healthy Volunteers n=15

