5.3 Inclusion criteria for Healthy Volunteers

- Age between 40 to 85 years, age and sex to match the group with IPF
- Healthy subjects without any diseases that may cause inflammation
- Women of childbearing age should not be pregnant, planning to get pregnant or breast-feeding.
- Currently non-smokers: see exclusion criteria

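### Healthy volunteers are matched to the IPF group on age and sex, but section 8.3 plans group tests with neither factor; if either predicts a marker, the IPF-versus-healthy blood and nasal comparison loses precision

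*Combined protocol and SAP*

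**What the plan says.** **Design.** Section 4.2 describes the controls as "Healthy volunteers (age/sex matched, non-smoking, without a clinical history of atopy". Section 5.3 words it as "Age between 40 to 85 years, age and sex to match the group with IPF". No pairs, matched sets, ratio, caliper or sampling rule is given. Section 8.2 gives the sizes: "The total study involves a total of 30 subjects with probable IPF, 15 patients with sarcoidosis and 15 healthy volunteers". Section 2 explains that healthy volunteers are included so that their blood and nasal levels can be compared with those of the patients. They give no bronchial samples.

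**Outcomes.** The first secondary outcome in section 3.3 compares airway mediator levels "within and across the 3 groups (probable IPF, sarcoidosis and healthy controls"; later ones extend the three-group comparison to blood and urine.

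**Analysis.** Section 8.3 says: "Paired or unpaired t-tests/ANOVA (or equivalent non-parametric tests) will be used to compare mediator levels in blood and airway mucosal lining fluid". These tests apply "within groups over time or between different groups at a single time point". Among further methods it lists that "multivariate analyses and ROC curves will be used as appropriate", naming no covariate and no comparison. The threshold is a P "value of <0.05 is considered significant". No effect size, standard deviation or power is stated; section 8.1 declines a sample size calculation.

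**The concern.** The design restricts who may be a control in order to balance age and sex, and the named analysis then makes no use of either. Variation in a marker that is due to age and sex stays in the error term, although the matching was meant to remove its influence on the comparison. With only 15 controls, a real nasal or blood difference from IPF could be missed that the same data would show with two extra model terms. This comparison is the stated reason for recruiting healthy volunteers.

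**Working it through.** **Inputs from the protocol.** 30 IPF and 15 healthy (8.2); significance level 0.05 (8.3), taken as two-sided because sidedness is not stated.

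**Assumed, because the documents are silent.** R2, the share of log-level variance explained by age and sex, varied from 0 to 0.30; total SD set to 1; a true difference that the unpaired test detects with 80% power when R2 = 0. The plan has no power figure of its own to reproduce.

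**Which test applies.** 8.3 offers paired or unpaired forms. Pairing suits the within-group, over-time half of the sentence. Thirty patients against 15 controls with no pair identifiers leaves only the unpaired form between groups.

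**Step 1: unpaired standard error and reference difference.**
- SE_unpaired = sqrt(1/15 + 1/30) = 0.3162
- Difference = (1.960 + 0.842) x 0.3162 = 0.886 SD

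**Step 2: close matching.** Age and sex are then balanced between groups, so only residual variance contributes to the difference of means: SE_true = sqrt(1 - R2) x 0.3162. At R2 = 0.20:
- SE_true = 0.8944 x 0.3162 = 0.2828; ratio 0.3162/0.2828 = 1.118
- False-positive rate of the unpaired test = 2 x [1 - Phi(1.960 x 1.118)] = 2.8%
- Power, unpaired = Phi[(0.886 - 1.960 x 0.3162)/0.2828] = Phi(0.94) = 82.7%
- Power, adjusted = Phi(0.886/0.2828 - 1.960) = Phi(1.17) = 88.0%

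| R2 | SE overstated by | False-positive rate | Power unpaired | Power adjusted |
|---|---|---|---|---|
| 0 | 0% | 5.0% | 80.0% | 80.0% |
| 0.05 | 2.6% | 4.4% | 80.6% | 82.0% |
| 0.10 | 5.4% | 3.9% | 81.3% | 84.0% |
| 0.20 | 11.8% | 2.8% | 82.7% | 88.0% |
| 0.30 | 19.5% | 1.9% | 84.3% | 91.8% |

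**Step 3: simulation with close but imperfect matching.** 8,000 data sets per setting, difference 0.886 SD, each control within 3 years of an IPF patient and of the same sex; unpaired t-test against a linear model with group, age and sex.

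| R2 | False-positive rate, t-test | Power, t-test | Power, adjusted |
|---|---|---|---|
| 0 | 5.2% | 78.6% | 78.1% |
| 0.10 | 4.3% | 79.8% | 82.2% |
| 0.20 | 3.1% | 80.0% | 85.8% |
| 0.30 | 2.9% | 80.4% | 89.9% |

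At R2 = 0.20 the mean unpaired SE was 0.314 to 0.315 against a true value of 0.286 to 0.287, about 10% too large. Two further simulations with other close-matching schemes gave 0.315 against 0.285 with power 82.3% against 88.4%, and 0.316 against 0.283 with power about 85% against 88%. Both gave a false-positive rate of 2.9%.

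**Step 4: independent draws from similar age and sex distributions.** This is the loosest reading of matching to the group. At R2 = 0.20 two simulations gave unpaired SEs of 0.314 against true values of 0.315 and 0.321, with false-positive rates of 4.8% and 5.4%. The unpaired test is then correctly calibrated. Adjustment still raised power from 80% to 87% in one and from 80% to 86% in the other.

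**Step 5: cost when age and sex do not matter.** At R2 = 0, adjustment moved power from 78.6% to 78.1% under close matching (0.5 points) and from 80.4% to 78.3% under independent draws (2.1 points). Across the simulations the cost was about 0.5 to 2.5 points.

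**Dependence on the assumed difference.** By the step 2 formulas at R2 = 0.20, the gain is 9.2 points at 0.6 SD (47.2% to 56.4%) and about 3 points at 1.0 SD (91.1% to 94.2%).

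**The case against.** The strongest reply is that the protocol never says how matching is done. Section 4 recruits carers, partners and people answering advertisements, and section 5.3 asks only that age and sex match the group. If that yields two independent samples with similar distributions, the unpaired standard error is right and nothing is miscalibrated. This stands. A reader might infer that the plan's p-values and intervals are certainly too conservative; the documents do not support that, because it needs both close matching and an R2 above zero. What survives under either reading is the loss of efficiency when age or sex predicts the marker.

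Second, 8.3 allows multivariate analyses where appropriate, so adjustment is not ruled out. True, but the phrase stands in a list with heat maps, violin plots and clustering and commits to no covariate for any comparison.

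Third, R2 is unknown and may be small for these markers. Also true: at R2 = 0.05 the formula gain is 1.4 points, and at zero adjustment costs a little.

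Fourth, the comparisons are secondary, the study calls itself exploratory, and any miscalibration from close matching is conservative, so it adds no false positives. This limits the weight of the point. It is not a reason to leave out two variables that are already collected.

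**Conclusion.** The point holds as a cheap improvement to the secondary IPF-versus-healthy comparisons in blood and nasal fluid. At an assumed R2 of 0.20, leaving out age and sex costs about 3 to 7 power points at 30 against 15, for a difference the unpaired test would detect with about 80% power. If matching is close, the unpaired SE of the difference is also about 10% too large and the false-positive rate is about 3%. If matching means only similar distributions, the test is valid but less efficient. Near R2 = 0 there is no gain and a small cost. All sizes rest on the assumed R2, the assumed difference, a two-sided 5% level and simulated age and sex distributions.

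Four wider readings are not supported:
- **Primary outcome.** It compares IPF with sarcoidosis in bronchial fluid and involves no healthy volunteers.
- **Error bars in 8.3.** These are SEMs of single groups, which matching between groups does not make wrong. Only the SE, interval and p-value of the difference are at issue.
- **Urine.** The quoted sentence covers blood and airway fluid; for urine the gap is that no test is named.
- **Future sample sizes.** Matching does not bias a marker's raw SD, so later calculations based on it would not be distorted.

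Sarcoidosis patients are not matched, and section 5.2 admits them from age 18. In comparisons involving them the age and sex question is confounding, which is a separate matter.

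**What to change.** In section 8.3, state that comparisons involving healthy volunteers use a linear model on the log level with group, age (continuous) and sex. Where a rank method is needed, use a rank-based or proportional-odds model with the same terms. Report the adjusted IPF-minus-healthy difference with its 95% CI and keep the unadjusted test as supporting. Apply the same model to urine. A paired test is not the remedy, because no pairs are defined.

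Cost: a sentence or two in 8.3 and no new data, since sections 7.1 and 7.2 already collect date of birth and gender from patients and volunteers. The IPF-versus-healthy model gives up two degrees of freedom (43 to 41) and about 0.5 to 2.5 power points for markers unrelated to age and sex.

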4.3 Sampling

For patients diagnosed with probable IPF and Sarcoidosis, BAL will be collected on the day of their scheduled bronchoscopy. Blood, nasosorption (NS), and bronchosorption (BS) samples will also be collected. Furthermore, on the day of their optional 3 and 6 months follow up visits, we shall collect blood and nasosorption (NS) samples. ***It is important to stress that bronchosorption samples must be taken before BAL or bronchial biopsy samples.*** All patients will have had HRCT of the lung and lung function testing (spirometry and DLco) up to 3 months before bronchoscopy sampling. Healthy volunteers will have a single visit with blood and NS sampling - but no bronchial samples.

With regard to possible coronavirus (COVID-19) infection, this clinical research project will meet Policies and Procedures in conjunction with the NHS, Imperial College London and Public Health England (PHE) guidelines. This will include use of Personal Protective Equipment (PPE) with appropriate clinical facilities and procedures. Appropriate precautions will be taken with sample collection, handling and processing.

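### Section 8.3 plans no between-group comparison of change over time, so the optional 3- and 6-month samples cannot show whether IPF and sarcoidosis change differently

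*Combined protocol and SAP*

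**What the plan says.** Section 8.3 states: "Paired or unpaired t-tests/ANOVA (or equivalent non-parametric tests) will be used to compare mediator levels in blood and airway mucosal lining fluid", and limits those tests to comparisons "within groups over time or between different groups at a single time point". The significance rule is a P "value of <0.05 is considered significant", with no statement of sidedness. The only other provision is open-ended: "Other graphical and analyses methods like heat maps, violin plots, clustering, multivariate analyses and ROC curves will be used as appropriate". No longitudinal or mixed model is named, and Section 8 does not mention missing visits or an analysis set.

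The group sizes in Section 4.2 are "Probable Idiopathic Pulmonary Fibrosis (IPF), n=30" and "Sarcoidosis patients, n=15". Section 4.3 describes the repeat sampling: "on the day of their optional 3 and 6 months follow up visits, we shall collect blood and nasosorption (NS) samples". Section 7.1 describes the same two visits without calling them optional, and with the schedule in 7.1.1 it adds urine. Healthy volunteers attend once. Bronchosorption is scheduled at the baseline bronchoscopy only.

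**The concern.** Two of the three patient visits serve only to repeat blood, urine and nasal sampling, and Section 2 presents the biomarkers as useful for monitoring fibrosis and as different between the two diseases. A reader of the results will naturally ask whether a mediator moves in IPF and not in sarcoidosis. With the named tests, the only available answer is to compare one group's p-value with the other's. That is not a test of the difference, and with 30 and 15 patients the two p-values will often fall on opposite sides of 0.05 when the true changes are identical.

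A second, smaller issue is that a paired test needs the later sample. With optional visits, the within-group changes describe patients who came back, and the plan does not say how non-attendance will be handled or reported.

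**Working it through.** The plan gives no effect size, SD, power or attendance figure (Section 8.1 says a sample size calculation is not possible), so there is no stated figure to reproduce. Group sizes and the 0.05 level come from Sections 4.2 and 8.3. Everything else below is assumed and shown as a range. Tests are taken as two-sided.

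**1. Two within-group tests when both groups change equally.** For a true change of d (in SDs of change), the paired t-test has n − 1 degrees of freedom and noncentrality d√n. At d = 0.5 this is 0.5 × √30 = 2.74 for IPF and 0.5 × √15 = 1.94 for sarcoidosis, giving power of 0.754 and 0.438. The groups are independent, so P(IPF only) = 0.754 × (1 − 0.438) = 0.424 and P(sarcoidosis only) = 0.438 × (1 − 0.754) = 0.108. Discordance is the sum, 0.53.

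| Equal true change (SD of change) | Power, n=30 | Power, n=15 | Significant in IPF only |
|---|---|---|---|
| 0.3 | 0.355 | 0.190 | 0.29 |
| 0.5 | 0.754 | 0.438 | 0.42 |
| 0.8 | 0.988 | 0.821 | 0.18 |
| 1.0 | >0.99 | 0.949 | 0.05 |

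At an assumed 80% attendance (24 and 12 patients), IPF-only results occur in 25%, 42% and 28% of studies at 0.3, 0.5 and 0.8 SD. At 60% (18 and 9) the figures are 20%, 38% and 39%.

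**2. Low power or unequal sizes?** Splitting the same 45 patients 22/23 gives powers of 0.609 and 0.630 at 0.5 SD, so discordance is 0.609 × 0.370 + 0.630 × 0.391 = 0.47, against 0.53 with 30/15. At that effect, low power causes most of the discordance, and the 2:1 sizes decide which group tends to look significant. The sizes matter more at larger effects: at 0.8 SD, 22/23 gives 0.947 × 0.044 + 0.956 × 0.053 = 0.09, against 0.19 with 30/15.

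**3. The direct contrast.** The standard error of the difference in mean change, in SDs of change, is √(1/30 + 1/15) = 0.316. A two-sample t-test on change has 34% power for a difference of 0.5 SD. The difference detectable with 80% power is 0.91 SD with full attendance, 1.02 SD at 80% (24 v 12) and 1.19 SD at 60% (18 v 9). The 95% CI half-width with full attendance is about 2.017 × 0.316 = 0.64 SD.

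**4. Precision lost by using returners only.** A baseline-to-6-month paired test at 80% attendance uses 0.8 × 30 = 24 patients. In simulation (n=30, three visits, correlation 0.6 between visits, random non-attendance), the SE of the 6-month change in SDs of level was 0.186 for the paired test and 0.181 for maximum likelihood. The variance ratio is (0.186/0.181)² ≈ 1.05. Only an analysis requiring both follow-up visits, as classical repeated-measures ANOVA would, loses more: it keeps about 0.8 × 0.8 × 30 = 19 patients, with SE 0.208 and ratio (0.208/0.181)² ≈ 1.32.

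**5. Bias.** With equal correlation 0.6 between visits and attendance driven by baseline level, the mean change among attenders is the true change minus (1 − 0.6) times their mean baseline deviation. If the log-odds of attending fall by 1 per SD of baseline, attenders average about −0.18 SD at 80% attendance and −0.26 SD at 70%. A true 0.50 SD (of level) is then estimated as 0.50 + 0.4 × 0.18 = 0.57 or 0.50 + 0.4 × 0.26 = 0.60. A regression using all baseline and month-3 data recovered 0.50 under this type of mechanism. If attendance depends only on the month-3 level, the paired estimate is unbiased under the same correlation structure (0.50).

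**The case against.** The strongest objection is that the protocol never asks this question. The primary outcome (Section 3.2) compares bronchial levels taken at baseline. None of the three research questions (3.1) or four secondary outcomes (3.3) mentions change over time, still less a difference in change. The study is exploratory, and the direct contrast would be imprecise. All of this stands, and it limits the importance of the point. It does not remove the gap: Section 8.3 itself plans over-time comparisons, and Section 8.1 hopes the data will support sample sizes for future studies. An estimated difference in change with its interval serves that aim better than two p-values.

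It can also be said that 8.3 names ANOVA and allows multivariate methods as appropriate, so a suitable model is not forbidden. That is true, but none is specified, and the stated scope of the named tests leaves out a between-group comparison of change.

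Two stronger readings are tempting. A reader might infer that the sponsor intends to claim disease-specific change from paired p-values; the documents announce no such claim. A reader might also infer that optional visits make the over-time results seriously imprecise or biased. The documents give no attendance rate or mechanism, the simple paired test loses little precision, and the bias may be nil. That only attenders are used is itself a consequence of the named tests, not a rule the plan states.

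**Conclusion.** The point holds as a modest improvement to the over-time analysis of blood and nasal mediators. As written, the plan offers no comparison of change between IPF and sarcoidosis. Inferring one from two within-group tests would give a spurious IPF-only result in roughly 5% to 42% of studies per mediator, for equal changes of 0.3 to 1.0 SD with full attendance. These figures rest on assumed effects, two-sided 0.05 tests, normally distributed changes and equal SDs of change in the two groups. The cost of relying on returners is secondary: a variance ratio of about 1.05 under the assumptions shown, and bias only where attendance depends on mediator level in particular ways. The primary outcome is untouched.

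**What to change.** In Section 8.3, for patients' blood and nasosorption mediators, replace the over-time paired tests with one mixed model per mediator on log level. Fixed effects are diagnosis, visit (baseline, 3 and 6 months) and diagnosis-by-visit. Within-patient covariance is unstructured, or a patient random effect if that does not fit. Include every patient with at least one sample.

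Report the within-group changes and the IPF minus sarcoidosis difference in change with 95% CIs. Present the difference as estimation, since only about 0.9 to 1.2 SD is detectable at 80% power for attendance between 100% and 60%. Report attendance by group and visit. Keep healthy volunteers in the single-visit comparison only. Sections 4.3 and 7.1 should also be reconciled on whether the follow-up visits are optional.

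The cost is a little more analysis work, with no new patients, samples or visits. The model assumes that non-attendance is missing at random given the observed levels, and this should be stated.
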